8.2.6. The percentage of liver histologic responders

Responders:

- The subjects who have an improvement in liver fibrosis by ≥ 1 stage with no worsening of steatohepatitis (no worsening of lobular inflammation or hepatocyte ballooning or steatosis grade) from baseline to Week 24.
- The subjects who have complete resolution of NASH (defined as an NAS score of 0 or 1 for inflammation and 0 for ballooning) with no worsening of fibrosis (i.e., no progression of NASH CRN fibrosis stage) from baseline to Week 24.

The difference between proportions observed in each treatment group, along with 95% CIs for the difference between proportions, will be presented. The percentage of responders in each treatment group will be compared using a chi-square test. Fisher exact test will be used if 50% of the cells have expected counts less than 5.

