**9.9 Clinical Evaluations****9.9.1 Liver Biopsy**

Subjects who meet the Screening criteria of an available liver biopsy tissue specimen within 6 months of Screening for the double-blind cohort and 12 months for the single-blind open-label cohort will not be required to undergo a liver biopsy. For the dosing Groups 3 or 4 of the open-label single-blind cohort and for the placebo-controlled 24-week histology cohort, the liver biopsy must be performed within 3 months of Screening in order to serve as the Baseline comparison for the additional Week 12 biopsy. All other subjects will be required to undergo a liver biopsy per the study site's local standard-of-care procedure during the Screening period and prior to randomization. Tissue from all subjects will be prepped and read by a qualified pathologist for review for the absence/presence of NASH. Liver biopsies

with histologically confirmed NASH will be further assessed by a qualified pathologist using the NAS and Fibrosis Score established and validated by the NASH Clinical Research Network (see [Appendix A](#)). Liver biopsies will be assessed for degree of steatosis (0–3), lobular inflammation (0–3), hepatocellular ballooning (0–2), and fibrosis (0–4). The first three components will be added together to determine the NAS that ranges from 0 to 8. Liver biopsies with a NAS of <4 will be considered exclusionary. Subjects with liver biopsies with Stage 0 (no fibrosis) or Stage 4 fibrosis (cirrhosis) will be excluded from this study. For the placebo-controlled 24-week histology cohort, only subjects with Stage 2 or Stage 3 fibrosis will be allowed to enroll into the study.

The Screening and EOT biopsies for dosing Groups 3 or 4 of the open-label single-blind cohort and all subjects in the placebo-controlled 24-week histology cohort will be read by a single central pathologist. The biopsies will be read and scored using the same NASH Clinical Research Network (CRN) scores as the inclusion biopsies. These will be read unpaired and blinded to subject and reported separately from the inclusion biopsy.

For the placebo-controlled 24-week histology, only the Week 24 biopsy results will be blinded to the site and subject. Screening biopsy results will not be blinded. The Week 24 biopsy should be obtained before the last dose of NGM282 with a visit window of -7 days and +3 days.

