## 12.2 Randomization and Enrollment

For the double-blind cohort, at Day 1 all eligible subjects will be randomized via IWRs to one of the three treatment arms (NGM282 3 mg, NGM282 6 mg, or placebo) in a 1:1:1 ratio. The proportion of subjects with diabetes (categorized on a dichotomous scale) will be balanced across the three groups to ensure an even distribution across the three groups.

Diabetes status for balancing (“no diabetes” or “diabetes”), will be based on medical history, Screening labs, current medications, and clinical assessments.

The single-blind cohort is not randomized. Subjects will initially be enrolled sequentially into dosing Group 1 and enrollment will be continuous within and between each dosing groups. Sequencing of the dosing Groups 2 and 3 will be based on PD and safety parameters from dosing Group 1 and may run in parallel to each other. A fourth optional dosing group may be conducted based on the safety/tolerability, imaging data and histology (dosing Group 3 only) data from the prior 3 dosing groups. Dosing Group 4 will be initiated only after all subjects in Cohort 3 have been enrolled and a minimum of 10 subjects have completed 12 weeks of treatment in order to do a preliminary review of key data. Dosing group sequence and individual subject treatment assignment will be blinded only study subjects throughout the study period.

For the placebo-controlled 24-week histology cohort, at Day 1 all eligible subjects will be randomized via IWRS to one of the two treatment arms (NGM282 1 mg or placebo) in a 2:1 ratio. The Sponsor, study sites, and subjects will be blinded to treatment assignment. The randomization schedule will be stratified by subject’s fibrosis stage 2 or 3 based on the screening qualification liver biopsy.

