### **12.9.3 Analysis of Secondary Endpoints**

The analysis of secondary PD endpoints will be based on the Efficacy population, for all three cohorts separately.

For continuous secondary endpoints the same method of analysis as for the primary endpoint will be followed. Further covariates/cofactors may be included in the modeling depending on the relevance to the endpoint analyzed and will be further described in the SAP.

Categorical secondary endpoints (percentage of normalization) will be analyzed through a chi-square test. The difference between proportions along with 95% CIs for the difference between proportions will be presented by treatment-group comparisons.

The analyses in the open-label single-blind cohorts will be stratified by statin use at Baseline whereas they will be stratified by fibrosis stage in the placebo-controlled 24-week histology cohort. The effect of statin use on lowering LDL cholesterol will also be explored both the open-label single-blind and placebo-controlled 24-week histology cohorts. In addition, sensitivity analyses will be performed to investigate the effect on the efficacy endpoints of statin use in the open-label single-blind cohorts and fibrosis stage on the placebo-controlled 24-week histology cohort.

Comparisons between the 3 cohorts will be performed and further detailed in the SAP.

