8.2. SECONDARY EFFICACY/PD ENDPOINT(S) AND ANALYSES

The main analysis population for secondary efficacy endpoints is the Efficacy Population. The analysis will also be repeated for the Per Protocol population and for subjects who completed their Week 24 assessment (completers) only.

8.2.1. The actual and percentage change from baseline in liver fat content by Magnetic Resonance Imaging-proton Density Fat Fraction. MRI-PDFF at Weeks 6, 12, 24, and 30

The observed values and changes from baseline will be summarized at Weeks 6, 12, 24, and 30, by NGM282 treatment group and fibrosis stage. The actual change and percentage change in absolute liver fat content from baseline to Week 6, Week 12, Week 24 and Week 30 will be compared between treatment groups using an analysis of covariance (ANCOVA) model with treatment group and fibrosis stage at baseline as cofactors and baseline endpoint and baseline ALT as covariates. Least square means with standard errors (SE), differences in least square means with SE, 95% CIs for the difference in least square means, and corresponding p-values will be presented.

The assumptions of normality will be evaluated. If the assumptions of normality are not satisfied, a rank ANCOVA method will be performed in addition to the parametric model.

The rank ANCOVA is a non-parametric statistical method described in Stokes, Davis, and Koch, 2000. It can be considered as an extension to the Wilcoxon rank-sum test with the ability to adjust for covariates and cofactors in the model. The mean, median and p-value for the actual change will be presented.

8.2.2. The percentage of normalization in absolute liver fat content at Week 24

Normal liver fat content normalization will be defined as $\leq 5.0\%$. Percent of subjects with normalized liver fat content will be presented by treatment group and fibrosis stage and will be analyzed through a chi-square test. The difference between proportions observed in each treatment group, along with 95% CIs for the difference between proportions, will be presented for all pairwise comparisons of treatment

Amendment Final V 2.0

groups. Fisher exact test will be used if 50% of the cells have expected counts less than 5.

8.2.3. The percentage of responders (based on a liver fat content decrease $\geq 5\%$, and relative decrease $\geq 30\%$)

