The percentage of responders will be analyzed through a chi-square test. The difference between proportions observed in each treatment group, along with 95% CIs for the difference between proportions, will be presented for all pairwise comparisons of treatment groups. Fisher exact test will be used if 50% of the cells have expected counts less than 5.

[REDACTED]

[REDACTED]

[REDACTED]

8.2.4. The actual and percentage changes from baseline by Week 24 of AST, ALT, bilirubin (total, direct), triglycerides and GGT.

The actual and percentage changes from baseline will be summarized by treatment group. An ANCOVA model as stated in 8.2.1 will be used to compare between treatment groups.

In addition, the percentage of subjects with AST, ALT, Total Bilirubin, Direct Bilirubin, Triglycerides, and GGT lab measurements within the normal range will be summarized by lab parameter, treatment group and visit. All pairwise treatment group comparisons of the proportion of subjects within the normal range will be tested using a chi-square test. Fisher exact test will be used if 50% of the cells have expected counts less than 5.

[REDACTED]

8.2.5. The actual and percentage changes from baseline at Week 24 and EOS of the following parameters: Total cholesterol, HDL-cholesterol, LDL-cholesterol, and lipoprotein particles.

The actual and percentage changes from baseline will be summarized by treatment group and fibrosis stage. ANCOVA model as stated in 8.2.1 will be used to compare between treatment groups. The ANCOVA model as stated in 8.2.1 will be used to compare the two treatment groups.

Amendment Final V 2.0

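### SAP 8.2.2 and 8.2.6 test proportions without stratifying by fibrosis stage, although randomisation is stratified by stage and protocol 12.9.3 says this cohort's secondary analyses will be too

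*SAP*

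**What the plan says.** - **Randomisation.** Protocol 12.2 allocates 2:1, stratified by "fibrosis stage 2 or 3 based on the screening qualification liver biopsy".
- **Protocol analysis.** Section 12.9.3 states "Categorical secondary endpoints (percentage of normalization) will be analyzed through a chi-square test". Later in the same section it says of the analyses that "they will be stratified by fibrosis stage in the placebo-controlled 24-week histology cohort". It names no stratified test. It then adds separate sensitivity analyses on the effect of fibrosis stage in this cohort.
- **SAP, means.** The ANCOVA in 8.2.1 has "treatment group and fibrosis stage at baseline as cofactors and baseline endpoint and baseline ALT as covariates".
- **SAP, proportions.** In 8.2.2, fat normalisation "will be presented by treatment group and fibrosis stage and will be analyzed through a chi-square test". In 8.2.6, histologic response: "The percentage of responders in each treatment group will be compared using a chi-square test". Both fall back on Fisher's test when expected counts are small. In 8.2.3, the readable text says "The percentage of responders will be analyzed through a chi-square test", and the normal-range comparisons in 8.2.4 are handled the same way. Redacted text follows both 8.2.3 and 8.2.4 and may add to them.
- **SAP section 11** (changes from the protocol) reads NA, and SAP 6.6 (subgroups) says not applicable.
- **Reads of the screening biopsy.** Protocol 9.9.1 has a single central pathologist read the screening and end-of-treatment biopsies: "These will be read unpaired and blinded to subject and reported separately from the inclusion biopsy".

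**The concern.** The SAP carries the randomisation stratum into the analysis of means but not into the tests of proportions, gives no reason, and declares no departure from protocol 12.9.3. Histologic response is a secondary endpoint, but it is the one on which this cohort was sized.

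Two things could be at stake. The first is efficiency: when stage is prognostic and randomisation balances it, an unstratified test carries between-stage variation in its error term, so it rejects less often than its nominal level and can lose power. The second is analyst choice: the SAP does not say whether the main result is the stratified or the plain one, and a reader comparing it with the protocol could expect either.

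The stratum itself is not pinned down. Randomisation uses the qualifying read, the ANCOVA uses stage at baseline, and a separate central read of the same screening biopsy will exist. The SAP 6.2.1 baseline rule (last assessment on or before first dose) cannot choose between two reads of one biopsy.

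**Working it through.** **Inputs.** Response 50% against 15%, two-sided 5%, 80% power, 2:1 allocation, 15% dropout, 50 + 25 planned (protocol 12.1; SAP 3.5 and 6.1). The documents give no stage-specific response rates and no expected stage mix, so both are assumed below.

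**Step 1: reproduce the plan's sample size.** With pooled variance and no continuity correction, the pooled rate is (2 × 0.50 + 0.15)/3 = 0.3833, and

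n(placebo) = [1.960 × √(1.5 × 0.3833 × 0.6167) + 0.8416 × √(0.15 × 0.85 + 0.50 × 0.50/2)]² / 0.35² = 20.6, so 21.

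That gives 21 + 42 = 63 evaluable. Then 63/0.85 = 74.1, which rounds up to 75 in the 2:1 ratio (25 + 50). The plan's figure reproduces, on an unstratified comparison.

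**Step 2: power with and without stratification.** All pairs of 2×2 tables were enumerated exactly for 42 active and 21 placebo, comparing Pearson chi-square with CMH (no continuity correction). For each assumed stage odds ratio (OR), the same in both arms, stage rates were solved so that the overall rates stay at 50% and 15%. For example, OR 3 with near-equal strata gives 63.4%/36.6% on active and 21.2%/8.2% on placebo.

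| Strata (active/placebo) | Stage OR | Chi-square | CMH | Difference (points) |
|---|---|---|---|---|
| Near-equal (21/11, 21/10) | 1 | 82.3% | 81.3% | -1.1 |
| | 2 | 82.6% | 83.1% | +0.5 |
| | 3 | 82.9% | 84.8% | +1.9 |
| | 6 | 83.7% | 88.4% | +4.7 |
| 2:1 (28/14, 14/7), larger stratum responds more | 1 | 82.3% | 81.6% | -0.8 |
| | 2 | 82.5% | 82.4% | -0.1 |
| | 3 | 82.8% | 83.4% | +0.6 |
| | 6 | 83.4% | 85.5% | +2.1 |

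Differences were taken before rounding.

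**Step 3: rejection rate when there is no treatment effect** (assumed stage rates, same in both arms).

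| Stage rates | Stage OR | Strata | Chi-square | CMH |
|---|---|---|---|---|
| 15%/15% | 1 | near-equal | 4.6% | 4.5% |
| 30%/20% | 1.7 | near-equal | 4.8% | 5.0% |
| 50%/10% | 9 | near-equal | 3.1% | 5.0% |
| 50%/10% | 9 | 2:1 | 3.5% | 5.0% |

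The plain test stays below 5% in every row. It becomes clearly conservative only when stage is strongly prognostic. The 50%/10% rows have a larger stage effect (OR 9) than any row of the power table.

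**Step 4: compare the texts.** If stratified in protocol 12.9.3 means a stratified test, then 8.2.2 and 8.2.6 both depart from it. If it means results shown by stage, 8.2.2 complies but 8.2.6 does not, because its text neither tests nor presents by stage. So 8.2.6 departs on either reading, and section 11 does not say so.

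**The case against.** The strongest reply is that the SAP uses the very test the protocol names. Section 12.9.3 specifies chi-square, and its stratification sentence may describe tabulation only: the same sentence stratifies the open-label cohort by baseline statin use, although that cohort is not randomised, and the effect of stage is then assigned to sensitivity analyses. On that reading 8.2.2 complies. By-stage responder tables may also sit in the redacted index of tables or in the separate mock-ups.

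The stakes are also modest. These are secondary endpoints, protocol 12.3 states a formal hypothesis only for liver fat in the double-blind cohort, and section 12 calls the general approach descriptive. Whether stage predicts response here is unknown, and if it does not, CMH costs about 1 point of power.

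Much of this stands. The ambiguity starts in the protocol, the plain test is valid, and the gain is small for moderate stage effects. The tabulation reading does not cover the text of 8.2.6, however. It also leaves unexplained why means are adjusted for the stratum and proportions are not.

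**Conclusion.** The concern holds. SAP 8.2.2 and 8.2.6 specify unstratified tests in a cohort randomised by fibrosis stage, against a protocol statement that its secondary analyses will be stratified by stage, and no change is declared. The same is true of the readable text of 8.2.3 and 8.2.4, subject to the redactions.

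The consequence is moderate. Type I error is not inflated and the sample size of 75 is unaffected. Using CMH would change power by about -1 to +5 points, and by about 1 point or less up to a stage OR of 2 (near-equal strata) or 3 (2:1 strata). These figures assume 42 and 21 evaluable patients, overall rates of 50% and 15%, a common stage OR in both arms, and the two stage mixes shown. The change is worth making because it is cheap and matches the analysis to the randomisation. The unspecified source of the stage variable is a missing detail to settle at the same time; the conclusion does not depend on it.

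**What to change.** 1. In SAP 8.2.2 and 8.2.6, and in 8.2.3 and 8.2.4 unless the redacted text already does so, specify a Cochran-Mantel-Haenszel test and a stratum-weighted risk difference with 95% CI, stratified by fibrosis stage as randomised (the screening qualification read). Name an exact stratified version for sparse tables.
2. State that the ANCOVA in 8.2.1 uses the same stage variable.
3. If the plain chi-square is kept as the main test, list it in section 11 as a change from protocol 12.9.3, with the reason.
4. As a minor clarification, 8.2.6 lists two responder definitions and then one test. State that the endpoint matching the 50% against 15% sizing is met when either definition is met, as in protocol 12.1, and report each component separately.

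The cost is SAP wording and one procedure option. The stratum is already recorded at randomisation, so no patients or procedures are added. The downside is about 1 point of power if stage turns out not to be prognostic.

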8.2.7. Other Secondary Endpoints

The actual and percentage changes from Baseline at Week 24 of the following parameters: [REDACTED], PRO-C3, ELF score, Fasting blood glucose, insulin levels, HbA1c, [REDACTED] [REDACTED], and HOMA-IR, Body weight, BMI, and waist circumference, C4 and serum bile acids, Bile-mediated absorption as measured by vitamin D, INR, and fecal fat content.

The actual and percentage changes from baseline will be summarized by NGM282 treatment group. ANCOVA model as stated in 8.2.1 will be used to compare between treatment groups.

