#### Open-Label Single Blind Cohort:

- a. NAS of at least 4 with 1 point in each component
- b. Histologic evidence of fibrosis without cirrhosis
  - i. Fibrosis stage 1-3
- c. Liver biopsy within 12 months of Screening.
  - i. Dosing Groups 3 or 4 must have a liver biopsy within 3 months of Screening in order to serve as the baseline comparison for the additional EOT biopsy.

Placebo-Controlled 24 Week Histology Cohort:

- a. NAS of at least 4 with 1 point in each component
- b. Histologic evidence of fibrosis without cirrhosis
  - i. Fibrosis stage 2-3
- c. Liver biopsy within 3 months of Screening in order to serve as the baseline comparison for the additional EOT biopsy.

3. Total liver fat content of  $\geq 8\%$  as measured by MRI-PDFF (MRI may be used for up to 8 weeks from the date of the original scan, including use for re-screened subjects)
4. Insulin-resistant or stable T2D

Double-Blind Cohort:

- a. Stable T2D is defined as HbA1c  $\leq 8.5\%$  at Screening.
- b. Diabetes medications: require a stable regimen for at least 3 months prior to Day 1 and throughout the study.
- c. Insulin resistance will be based on fasting insulin level  $\geq 10\text{uIU/mL}$ .

Open-Label Single Blind:

- a. Stable T2D is defined as HbA1c  $\leq 9.5\%$  at Screening.
- b. Diabetes medications (except GLP1 agonists): require a stable regimen for at least 3 months prior to Day 1 and throughout the study.
- c. GLP1 agonists: require a stable regimen for at least 12 months prior to Day 1 and throughout study
- d. Insulin resistance will be based on fasting insulin level  $\geq 10\text{uIU/mL}$ .

Placebo-Controlled 24 Week Histology Cohort:

Patients with T2D or insulin resistance will be allowed to enroll under the following conditions listed below and patients who do not have T2D or insulin resistance can be enrolled as long as all other criteria are met.

- a. HbA1c  $\leq 9.0\%$  at Screening
- b. Patients taking diabetes medications (except GLP1 agonists) require a “stable” regimen for at least 3 months prior to Day 1 and throughout study.
  - i. GLP1 agonists and pioglitazone: require a stable regimen for at least 12 months prior to Day 1 and throughout the study.

- ii. Stable insulin dosing is defined as reasonable dosage adjustments to maintain glucose control.

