## 9.7 Prior and Concomitant Medications

Concomitant therapies are any prescription or over-the-counter preparations used by a subject while participating in this study and must be recorded from 28 days prior to Day 1 until end of study.

Subjects should refrain from the use of any new medications or products or change in the dose or frequency of existing therapies during Screening and throughout the study. The Medical Monitor should be informed of any changes or addition of medications during this time period.

**Prohibited Medications** from 28 days prior to Day 1 and throughout study:

- Investigational agents, other than NGM282, or devices for any indication
- Known hepatotoxic agents
- Agents used for the treatment of any condition listed in the exclusionary enrollment criteria (see [Section 8.1.2](#))
- Any hepatotoxic herbal medications other than standard vitamin supplements

Placebo-Controlled 24 Week Histology Cohort Only:

- Investigational agents, other than NGM282, or devices for any indication
- Agents used for the treatment of any condition listed in the exclusionary enrollment criteria (see [Section 8.1.2](#))
- Hepatotoxic agents outlined in ([Appendix E](#)).
  - All other hepatotoxic agents will be left to the discretion of the PI. There should be clear documentation in the patient study records of PI approval of use.

**Prohibited Medications** within 3 months of Screening and throughout study:

- Ezetimibe, colesevelam, cholestyramine, niacin, PCSK9 inhibitors, or other lipid-lowering agents (except Double-blind)

Placebo-Controlled 24 Week Histology Cohort Only:

- Contraindicated medications according to rosuvastatin package insert ([Appendix C](#))
  - Includes cyclosporine, gemfibrozil, protease inhibitors (atazanavir, ritonavir, lopinavir, simeprevir), coumarin anticoagulants, fenofibrates, niacin and colchicine
- Contraindicated medications according to ezetimibe package insert ([Appendix D](#))
  - Includes cyclosporine, fenofibrate, cholestyramine and coumarin anticoagulants

- Use of any other lipid lowering agents or combination preparation of statins, within 3 months of Screening and throughout study, **except** ezetimibe when approved by MM/designee as second line lipid management therapy.
  - colesevelam, cholestyramine, niacin, PCSK9 inhibitors (evolocumab or alirocumab), colestid, fibrates, fenofibrates, pharmacologic/prescribed fish oil

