5.3. EFFICACY POPULATION

The Efficacy Population will include all enrolled subjects who receive at least one dose (full or partial) of NGM282 and have at least one valid, non-missing post-dose efficacy/PD parameter value.

All efficacy and PD endpoints will be summarized and analyzed using the Efficacy population. This will be the main population for the analysis of efficacy and PD endpoints. The Efficacy population will be based on enrolled treatment if this differs from actual treatment received.

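### Fasting insulin and HOMA-IR are analysed in the whole Efficacy population, although the 24-week cohort admits insulin-treated patients whose dose may change on study, so change in HOMA-IR does not isolate insulin sensitivity

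*SAP*

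**What the plan says.** **Endpoints and model.** SAP 8.2.7 takes actual and percentage change from baseline at Week 24 in a list that includes "Fasting blood glucose, insulin levels, HbA1c" and, further on, "and HOMA-IR, Body weight, BMI, and waist circumference". It then states: "ANCOVA model as stated in 8.2.1 will be used to compare between treatment groups". The terms of that model in SAP 8.2.1 are "treatment group and fibrosis stage at baseline as cofactors and baseline endpoint and baseline ALT as covariates". There is no term for insulin use or diabetic status. Protocol 12.9.2 confines its diabetic-status cofactor to the double-blind cohort.

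**Analysis set.** SAP 5.3: "All efficacy and PD endpoints will be summarized and analyzed using the Efficacy population". SAP 8.2 repeats the secondary analyses in the Per Protocol population and in Week 24 completers.

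**Who may enter.** For the 24-week cohort, Protocol 8.1.1, criterion 4, says: "Patients with T2D or insulin resistance will be allowed to enroll under the following conditions listed below". For insulin it adds: "Stable insulin dosing is defined as reasonable dosage adjustments to maintain glucose control". Of the diabetes types, Protocol 8.1.2 excludes only type 1.

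**Dose changes in general.** Protocol 9.7 reads: "Subjects should refrain from the use of any new medications or products or change in the dose or frequency of existing therapies during Screening". That sentence goes on to cover the rest of the study, and changes are to be notified to the Medical Monitor.

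**Strata and subgroups.** Protocol 12.2 stratifies this cohort by fibrosis stage only. SAP 6.6 marks subgroups as not applicable.

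**The concern.** HOMA-IR is the protocol's estimate of insulin resistance, calculated from fasting insulin and glucose. That reading presupposes that fasting insulin reflects the subject's own secretion. In an insulin-treated subject both components also reflect the prescribed dose, and criterion 4 lets that dose move during the trial.

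The movement may depend on treatment. Protocol 5.1.3 reports improved insulin sensitivity and a trend to lower fasting glucose with NGM282 in type 2 diabetes. Protocol 9.9.4 blinds sites to ALT, AST and lipids from Week 2, but glucose is not on that list. An investigator may therefore adjust insulin in response to glucose values that the study drug has altered. Part of any between-arm difference in HOMA-IR could then be a difference in prescribing.

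A second cost is precision: if change is more variable in insulin users, they widen the interval for everyone. At stake is whether two secondary metabolic results from a cohort of 75 can be interpreted.

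**Working it through.** The plan states no figure on this point, so there is none to reproduce. The check has two parts.

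**1. Does anything in the readable text separate insulin users?**

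- *Baseline value as covariate (SAP 8.2.1).* It adjusts for where a subject started. It cannot adjust for a dose change made after baseline.
- *Rank ANCOVA when normality fails (SAP 8.2.1).* It limits the pull of extreme values. It does not remove a dose change that depends on treatment.
- *Per Protocol and completer repeats (SAP 8.2).* Protocol 12.4.5 excludes for deviations or adverse events judged to affect the primary endpoint. Insulin use is neither by definition.
- *Randomisation (Protocol 12.2).* Insulin use is not a stratum.
- *Missing-data rule (SAP 6.3).* Available data are used, with no rule for values affected by concomitant insulin.
- *Redactions.* Those in SAP 8.2.7 fall inside the parameter list; the sentence naming the analysis is intact.

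Nothing readable separates them.

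**2. How much precision could be lost?**

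Inputs, neither from the documents: share of insulin users q = 0.10 to 0.25; ratio r of the change SD in users to that in non-users = 2 to 3. The calculation takes the same mean change and the same user share in both arms, and ignores covariate adjustment.

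- Pooled SD relative to non-users: sqrt(1 − q + r²q)
- Widening from the smaller sample if users are dropped: 1/sqrt(1 − q)
- All-subject CI width relative to users excluded: the first divided by the second
- Narrowing on exclusion: 1 − 1/(that ratio)

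| q | r | Pooled SD ratio | Loss from smaller n | CI width, all vs excluded | Narrowing on exclusion |
|---|---|---|---|---|---|
| 0.10 | 2 | sqrt(1.30) = 1.14 | 1.05 | 1.08 | 8% |
| 0.25 | 2 | sqrt(1.75) = 1.32 | 1.15 | 1.15 | 13% |
| 0.10 | 3 | sqrt(1.80) = 1.34 | 1.05 | 1.27 | 21% |
| 0.25 | 3 | sqrt(3.00) = 1.73 | 1.15 | 1.50 | 33% |

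The gain in precision exceeds the loss of subjects in every row. If users were no more variable than non-users (r = 1), exclusion would simply widen the interval by 1.05 to 1.15 times. The confounding in part 1 does not depend on r and is not in the table.

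**The case against.** The case for leaving the plan alone has real content.

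- *Dose changes are already discouraged.* Protocol 9.7 asks subjects to refrain, and criterion 4 requires a regimen that is stable before and during the study, with only reasonable adjustments. This may limit how often doses move. It does not settle the matter, because the insulin definition counts adjustments as stable.
- *The size is assumed.* This stands. The share of users and the SD ratio are not in the documents, and the baseline covariate may absorb some of the spread.
- *Excluding insulin users can itself bias the comparison.* This stands for anyone who starts insulin on study. Starting may depend on treatment, so dropping those subjects or values conditions on a post-randomisation event. It does not apply to insulin use at baseline.
- *These are two of many secondary parameters.* True. The primary endpoint is MRI-PDFF, and the cohort's size rests on histologic response.

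A reader might also infer more than the documents support:

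- That the assay measures the injected insulin. The documents do not say. The concern survives without it, since titration alters glucose and the subject's own secretion.
- That SAP 6.6 forbids a separate look at insulin users. Not applicable is not a prohibition, and the SAP itself presents results by fibrosis stage.
- That both endpoints fail to measure what they claim. The plan claims only change in insulin levels for the first; HOMA-IR alone is named as an estimate of insulin resistance.
- That the SAP certainly contains no restriction. The Per Protocol definition, the exploratory section and the table index are redacted, so this holds for the readable text only.

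**Conclusion.** The point holds as a cheap and worthwhile improvement to two secondary analyses. The plan admits insulin-treated patients, allows their dose to move, and analyses fasting insulin and HOMA-IR in everyone with no provision for insulin use. In insulin users, change in HOMA-IR mixes insulin sensitivity with prescribing that may itself respond to treatment.

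The direction and size of any bias cannot be determined from the documents. The precision cost is conditional: an all-subject interval 1.08 to 1.50 times as wide, under 10-25% users and an SD ratio of 2-3. It would be wrong to read the upper figure as a 50% narrowing on exclusion; 1 − 1/1.50 is 33%.

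**What to change.** In SAP 8.2.7:

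1. Make the main analysis of fasting insulin and HOMA-IR the Efficacy-population subjects not on insulin at baseline. This criterion is fixed before randomisation.
2. Keep the all-subject analysis as a sensitivity analysis.
3. Add a supplementary analysis that excludes values after an on-study insulin start, showing the numbers excluded by arm.
4. Report insulin use by arm, and dose change if it is captured.
5. Keep fasting glucose and HbA1c in all subjects, read alongside the insulin-use summary, since dose adjustment affects them too.

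Define the baseline flag from medication dates that span Day 1. The concomitant category in SAP 7.4.2 is worded by start date, from 28 days before Screening, and could miss insulin begun earlier.

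In the protocol, criterion 4 of 8.1.1 (adjustments count as stable) and 9.7 (refrain from dose changes) must be reconciled.

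Cost: a short SAP paragraph and fewer subjects for two secondary endpoints. Concomitant therapies are recorded under Protocol 9.7, but the documents do not confirm that daily insulin dose is captured, so dose reporting depends on checking the case report form. The primary MRI-PDFF analysis does not change.
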